4.4.2 Cardiac MRI T2*

Cardiac MRI T2* will be evaluated as secondary endpoint and will be measured in patients aged 10 years or more and able to undergo the evaluation without being sedated.

Cardiac iron load will be assessed - adopting the Cardiac MRI T2*-based technology and protocol from Resonance Health Ltd. - at baseline, and after 6 and 12 months of treatment.

Cardiac MRI T2*, as a component of the composite endpoint, will be analysed as secondary endpoint with the intent of clarifying the interpretation of the composite (Turk DC et al, 2008). Cardiac MRI T2* will be analysed as a binary variable (with success defined as in **Section 4.3.1**, criterion B). Additional details on the analysis are reported in **Section 11.2** and **Section 11.4**.

4.4.3 Liver MRI

The efficacy of treatment in terms of LIC as measured by MRI will be a secondary endpoint and will be assessed in all patients able to undergo MRI scan without sedation.

Liver MRI will be assessed - adopting the Ferriscan® technology and protocol from Resonance Health Ltd. - at baseline and after 12 months of treatment.

Efficacy will be assessed in terms of percentage of successfully chelated patients. The criterion for success has been differently defined according to a threshold for baseline LIC. Success for patients with values of 7 mg/g dry weight or more will be defined as a reduction by 20% or more after 1 year treatment. Success for patients with a baseline less than 7 mg/g dry weight will be defined as a decrease in LIC, or if there is an increase in LIC, it will not be more than 15% after 1 year treatment despite continued transfusion with chelation therapy (**Table 2**).

Table 2. Definition of treatment success for liver MRI

Baseline LIC ≥ 7 mg/g dry weight	Reduction of 20% or more after 1 year treatment
Baseline LIC < 7 mg/g dry weight	Decrease in LIC or an increase ≤ 15% after 1 year treatment as long as the increase does not result in a LIC value > 7 mg/g dry weight

4.4.4 Safety and tolerability

Safety and tolerability assessments will consist of monitoring and recording all Adverse Events (AE) and Serious Adverse Events (SAE) as defined in **Section 16.1**, regular monitoring of haematology, blood chemistry and urine values, regular measurements of vital signs, performance of physical examinations, standard measures of growth and maturation.

4.4.5 Pharmacokinetics

Plasma samples will be collected at the end of treatment for the assessment of drug concentrations at steady-state conditions in all the patients until a patients' number leading to statistically significant analysis is reached. Pharmacokinetic data will then be analysed to confirm the influence of relevant covariates (e.g., demographics) on the systemic exposure to drug treatments.

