2. OBJECTIVES

2.1Primary Objective

The primary objective of this study is to assess the non-inferiority of deferiprone (DFP) compared to deferasirox (DFX) in terms of changes of ferritin levels and heart iron concentration in paediatric patients affected by hereditary haemoglobinopathies requiring chronic transfusions and chelation.

2.2Secondary objectives

Secondary objectives of this study are:

- to assess treatment efficacy in terms of ferritin levels
- to assess treatment efficacy in terms of cardiac MRI T2* in patients over 10 years of age able to perform MRI scan without sedation
- to estimate the efficacy of treatments in terms of liver iron concentration (LIC) measured by MRI in all paediatric subjects able to have MRI scan without sedation
- to evaluate the safety and tolerability profile of treatments
- to assess healthcare resources utilisation and patient global assessment, including compliance and quality of life (QoL) evaluation
- to confirm the influence of demographic covariates on the pharmacokinetic disposition of treatments across the study population.

2.3Exploratory objectives

Additional and exploratory objectives of the study include the assessment of the correlation between systemic exposure to the investigational drugs and serum ferritin levels observed after one year treatment.

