The target patient population consists of 388 outpatients affected by hereditary haemoglobinopathies requiring chronic transfusion and chelation, randomized 1:1 in two groups of 194 patients each to ensure 310 evaluable patients. Chelation naïve and not naïve patients aged from 1 month to less than 18 years will be recruited. A staggered approach will be applied to patients aged less than 6 years (10% of the total sample), which will be recruited after results from the PK Study (Study DEEP-1, EudraCT n. 2012-000658-67) will be available.

Experimental arm: patients administered with DFP at 75-100 mg/kg/day for seven days per week. In patients aged less than 6 years the dose will be defined according to the results of the PK Study (Study DEEP-1, EudraCT n. 2012-000658-67). DFP daily dose will not exceed 100 mg/kg.

Control arm: patients administered with DFX at 20-40 mg/kg/day as recommended by the currently approved European SmPC (last update 10/08/2011). DFX daily dose will not exceed 40 mg/kg.

Details on the starting dose and subsequent dose adjustments are reported in **Section 6**.

The **treatment duration** for both groups is 12 months.

4.1Non-inferiority margin

This study is designed to demonstrate the **non-inferiority** of a new liquid DFP (80 mg/mL) formulation in comparison with DFX in terms of percentage of successfully chelated patients as described in **Section 4.3**.

DFP will be declared non inferior to DFX if the lower limit of the 95% confidence interval for the difference in the proportion of successful chelation in the two groups is above -12.5%. The choice of this margin is based on clinical considerations starting from the available evidences for the effects of DFX at both ferritin and cardiac levels. For details please refer to **Section 11**.

4.2Choice of comparator

DFP will be compared to the oral chelating agent DFX. The rationale for comparing two oral chelators derives from the recent literature data reporting that oral chelating agents currently represent the most widespread adopted therapy in the paediatric age, due to good compliance, improved QoL and reduced burden of the disease (Ceci A et al, 2011).

4.3Primary endpoint

The primary endpoint will be the measure of treatment efficacy defined as the percentage of patients successfully chelated, as assessed by serum ferritin levels (in all patients) and cardiac MRI T2* (in patients above 10 years of age able to have an MRI scan without sedation).

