7.3.7 Pharmacokinetics

Pharmacokinetic assessment will be performed in patients who complete the study. Last dose of the study treatments (DFP and DFX) must be administered in the clinic under supervision of qualified staff at the beginning of the visit V15 and time of administration must be recorded accordingly and reported in the CRF. A sample (2 mL) for the assessment of peak drug concentrations should be collected within 4 hours after dosing according to the sparse sampling scheme specified in the SPM.

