11.2 Study population

Intent to treat population

For the intent to treat (ITT) analysis all patients that have been randomized and start therapy will be included.

Per protocol population

Patients in the per protocol (PP) population for the primary efficacy analysis (PP1) are those that have received the study drugs and for whom the composite endpoint is available at baseline and after 1 year treatment, without major protocol violations.

For the secondary efficacy evaluation assessed as non-inferiority of DFP to DFX in terms of serum ferritin levels the PP population (PP2) includes only patients for whom the measure of serum ferritin is available at baseline and after 1 year treatment.

For the secondary efficacy evaluation assessed as non-inferiority of DPF to DFX in terms of successfully chelated patients according to cardiac MRI T2* the PP population (PP3) includes only patients for whom the measure cardiac MRI T2* is available at baseline and after 1 year treatment.

Safety population

The population for the safety and tolerability analysis will include all patients having received at least one dose of study medication.

PK and PKPD population

The population for the pharmacokinetic and subsequent exploratory analyses (e.g. correlation between systemic exposure and ferritin levels) will include patients who have received the investigational drugs throughout the duration of the study (i.e., 1 year) and have had a blood sample collected for the assessment of drug concentrations in plasma.

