11.8 Pharmacokinetic evaluation

The objective of the pharmacokinetic analysis is to evaluate the influence of potential covariates (e.g., subject's demographics, disease status and concomitant medications) on the parameters of interest.

The data collected in this study will be enriched with data obtained during the DEEP-1 DFP pharmacokinetic study. Covariate effects will be assessed using non-linear mixed effects modelling. During each step in the covariate model building process, statistical diagnostic tools will be used to evaluate model performance.

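### Section 4.4.5 ends pharmacokinetic sampling at an unstated, significance-based number, while the visit schedule and Section 7.3.7 sample every completer

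*Combined protocol and SAP*

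**What the plan says.** Protocol Section 2.2 lists a secondary objective: "to confirm the influence of demographic covariates on the pharmacokinetic disposition of treatments across the study population". Section 4.4.5 describes the sampling. Plasma is taken at the end of treatment in all patients, but only until a patient "number leading to statistically significant analysis is reached". The next sentence reads: "Pharmacokinetic data will then be analysed to confirm the influence of relevant covariates".

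The operative sections set no such limit:

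- Section 7.2.4 lists pharmacokinetics among the V15 (month 12) assessments. Footnote 2 to Table 5 and Section 7.3.22 describe the sample without a cap.
- Section 7.3.7: "Pharmacokinetic assessment will be performed in patients who complete the study".
- Section 11.2: the PK and PKPD population "will include patients who have received the investigational drugs throughout the duration of the study" and who have a blood sample.

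On analysis, Section 11.8 states: "Covariate effects will be assessed using non-linear mixed effects modelling". It also states: "The data collected in this study will be enriched with data obtained during the DEEP-1 DFP pharmacokinetic study". Neither Section 11.8 nor Section 11.12 gives a PK sample size, a significance level or a threshold for including a covariate. Section 11.11 plans no interim analyses.

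Section 4 makes patients under 6 years 10% of the sample, "which will be recruited after results from the PK Study". Sections 5 and 6.6 make that share a minimum.

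**The concern.** A site or data manager cannot tell from the plan when PK sampling ends. One section has a stopping condition, and the sections that direct the visit have none.

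The wording of the condition matters as well. If sampling continues until a test is significant and then stops, the final test no longer has its nominal error rate, and a covariate effect can be confirmed by chance. If the phrase only means enough patients, the number should have been fixed beforehand, and it is not stated.

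There is also a question of who would be missed. PK is sampled only at month 12, so late entrants are sampled last. Patients under 6 are meant to enter late, and they form one end of the age range in an objective about demographic covariates across the whole study population.

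**Working it through.** **1. The plan's own sizes.** No PK number is stated, so the trial size is the only bound on the number of samples. Inputs from Section 11.12: success 65% (DFX) and 67.5% (DFP), one-sided 0.025, power 80%. The margin of 12.5 points is in Section 4.1.

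n per arm = (1.960 + 0.842)² × (0.65×0.35 + 0.675×0.325) / (0.125 + 0.025)² = 7.85 × 0.4469 / 0.0225 ≈ 156, or 312 in total. The plan says 310; power at 155 per arm is 79.8%. Dropout: 310 / 0.80 = 387.5, so 388. Both figures reproduce. They concern the primary endpoint and do not supply a PK number.

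**2. The literal reading.** The documents give no alpha or look schedule, so the following are assumptions: one covariate with no true effect, a two-sided 5% test of its correlation with exposure, and stopping at the first p < 0.05, in 20,000 simulated trials. The Monte Carlo standard error at 5% is √(0.05×0.95/20,000) ≈ 0.15 points.

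| Looks | One arm, maximum 155 | Both arms, maximum 310 |
|---|---|---|
| One fixed analysis | 4.9% | 5.1% |
| Every 50 patients | 11% | 16% |
| Every 20 patients | 17% | 23% |
| Every 10 patients | 23% | 29% |

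Two further schedules over 310 patients, using a z-test at 1.96, give about 14% (five looks) and 24% (29 looks, every 10 patients from 30). The range over 310 is therefore about 14–29%. The one-arm column suits an analysis by drug better, since the 310 column pools two drugs.

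With three independent null covariates over 310 patients, looks every 20 give 55%. One fixed analysis gives 14%, in line with 1 − 0.95³ = 14.3%.

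**3. The other reading.** If the number is fixed in advance from a precision or power target, the first row of the table applies and there is no inflation. The plan states no such number, and none can be derived, because it gives no PK effect size, variability or alpha.

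**4. Patients under 6.** 10% of 388 is about 39 enrolled; 10% of 310 is 31 evaluable, about 15–16 per arm. Assume all of them are sampled last. Stopping at or before 310 − 31 = 279 then includes none. Under the literal rule with one null covariate, this happens in 14% (looks every 50) to 28% (every 10) of simulated trials. Within one arm, stopping by 0.9 × 155 = 139.5 happens in 8% to 22%. A true covariate effect would stop sampling sooner.

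**The case against.** A reader might infer that the plan schedules repeated significance tests on accumulating PK data. It does not. Section 4.4.5 puts the analysis after collection, Section 11.11 plans no interim analyses, and no test, look or decision-maker is described. Enough patients for an adequate analysis is a fair reading of the clause. The planned method is also non-linear mixed effects modelling, not a repeated test of one correlation. All of this stands: the percentages illustrate one reading and do not estimate this trial's error rate. It does not rescue the clause, because the milder reading needs a number that the plan does not give.

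A reader might also infer that the under-6 group will be left out. The documents do not support that either. No early stop is scheduled. Section 20 agrees with Section 4 that these patients enter only after the DEEP-1 results, but the criterion in Section 5.1 reads as admitting some earlier. No DEEP-1 reporting date is given, so how far they would trail is unknown. For DFP, the DEEP-1 data largely answer the concern, since Section 3.3 takes the under-6 dose from that study. What remains is mainly DFX, for which no supplementary data are named.

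Finally, sites that follow the V15 schedule would sample every completer anyway. That is a good reason to remove the conflicting clause. Section 11.2 is weaker evidence of a conflict than Section 7.3.7: it sets no cap, but because it requires a sample to be present it could accommodate one.

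**Conclusion.** The point holds as a contradiction and an undefined stopping number. Section 4.4.5 ties the end of PK sampling to significance without giving a number or a threshold, while the V15 schedule and Section 7.3.7 sample all completers.

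Inflation is conditional on the literal reading and on the assumed 5% level and looks: about 14–29% over 310 patients or 11–23% within one arm, against about 5%. Under the milder reading, the defect is a number open to choice after data are seen. Thinning of the under-6 group is possible, not established, and matters mainly for DFX.

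Only the secondary PK objective and the exploratory PKPD analysis are affected. The primary non-inferiority test and the 310/388 size are not. The clause should be corrected, but it does not threaten the trial's main conclusion.

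**What to change.** In Section 4.4.5, delete the limiting clause (the one ending "number leading to statistically significant analysis is reached") and state that all completers are sampled at V15, as Section 7.3.7 provides and the population in Section 11.2 allows. Add to Section 11.8 that there will be one covariate analysis after all samples are collected, with the covariate-inclusion threshold set before the data are seen.

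If the sponsor wants fewer samples, the alternative is a number fixed in advance per arm, with a minimum for patients under 6, from a stated precision target.

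The preferred change deletes one clause and adds a sentence. It needs no visit, blood draw or procedure beyond those already in the V15 schedule, and it leaves the sample size unchanged.

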4.4.6 Healthcare Resources Utilisation

At each scheduled monthly visit the level of health care resources utilization in the previous month will be recorded. Specifically, the frequency and duration of inpatient hospitalization related to patient haemoglobinopathy will be recorded along with the primary reason for the hospitalization. For each hospitalization the duration spent in each of the following will be recorded: ICU, general ward, emergency room, other. Hospitalizations will be defined as any visit to the hospital requiring an overnight stay. The frequency of outpatient visits will be recorded along with the type of physician the patient saw and the type of visit. An outpatient visit will be defined as any visit to a medical practitioner or to a specialist not requiring an overnight stay. Any resource used in addition to those foreseen in the protocol will be recorded.

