- provide protective isolation; if clinically indicated, admit patient to hospital, obtain regular vital signs and treat the patient as per clinical need and per local protocol (antibiotic therapy and/or granulocyte colony stimulating factor).
- the patient will be examined the same day, if possible, collecting drug history and physical examination;
- if possible, hemoculture, viral studies (CMV, parvovirus, hepatitis A/B/C), serum ALT, BUN, creatinine will be collected.

Severe Neutropenia/Agranulocytos

- treatment must be interrupted immediately and the patient must be withdrawn from the study and monitored until resolution of the event;
- provide protective isolation; if clinically indicated, admit patient to hospital, obtain regular vital signs and administer appropriate therapy such as antibiotic therapy and granulocyte colony stimulating factor, beginning the same day that the event is identified;
- the patient will be examined the same day, if possible, collecting drug history and physical examination;
- if possible, hemoculture, viral studies (CMV, parvovirus, hepatitis A/B/C), serum ALT, BUN, creatinine will be collected.
- the patient will be monitored daily or more frequently until two successive ANCs are $\geq 1500/\text{mm}^3$.

All neutropenia, irrespective of their severity or seriousness must follow the expedite reporting of SAE, as indicated in Section 16.6 “Instructions for rapid notification of Neutropenia”.

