7.3.28 Healthcare Resources

Healthcare resources as reported in **Section 4.4.6** will be assessed at each monthly visit from V4 to V15 and the following parameters will be recorded in the CRF: hospitalisation (ward, length of hospitalisation), outpatient visits (type of visit), tests performed outside those foreseen in the protocol.

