11.10 Health Care Resources Utilisation

The level of resource utilization in each treatment group will be summarized but will not be subjected to inferential statistics.

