16.1 Definitions

In this trial protocol the definitions reported in **Table 8** apply according to the Art.2 of the Directive 2001/20/EC.

Table 8. Definitions

TERM	DEFINITION
‘Adverse Event’ (AE)	any untoward medical occurrence in a patient or clinical trial subject administered a medicinal product and which does not necessarily have a causal relationship with this treatment ^A
‘Adverse Reaction’ (AR)	all untoward and unintended responses to an investigational medicinal product related to any dose administered
‘Serious Adverse Event or Serious Adverse Reaction’ (SAE or SAR)	any untoward medical occurrence or effect that at any dose: 
 ▪ results in death ▪ is life-threatening^B ▪ requires hospitalisation or prolongation of existing hospitalization^C ▪ results in persistent or significant disability or incapacity^D ▪ is a congenital anomaly or birth defect ▪ other medically important/clinically significant events^E
‘Unexpected Adverse Reaction’ (UAR)	an adverse reaction, the nature or severity of which is not consistent with the applicable product information (e.g. Investigator's brochure for an unauthorised investigational product or summary of product characteristics for an authorised product)

^AAn AE can therefore be any unfavourable and unintended sign (including an abnormal laboratory finding), symptom, or disease (new or exacerbated) temporally associated with the use of a medicinal product.

^BThe term 'life-threatening' in the definition of 'serious' refers to an event in which the subject was at risk of death at the time of the event. It does not refer to an event, which hypothetically might have caused death, if it were more severe.

^c In general, hospitalization signifies that the subject has been detained (usually involving at least an overnight stay) at the hospital or emergency ward for observation and/or treatment that would not have been appropriate in the physician's office or outpatient setting. Complications that occur during hospitalization are AEs. If a complication prolongs hospitalization or fulfils any other serious criteria, the event is serious. When in doubt as to whether "hospitalization" occurred or was necessary, the AE should be considered serious.

Hospitalization for elective treatment of a pre-existing condition that did not worsen from baseline is not considered an AE.

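### Section 4.4.6 limits recorded hospital stays by an undefined link to the haemoglobinopathy, so admissions for chelator toxicity may be recorded inconsistently

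*Combined protocol and SAP*

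**What the plan says.** Resource use belongs to a secondary objective in Section 2.2: "to assess healthcare resources utilisation and patient global assessment, including compliance and quality of life (QoL) evaluation". Section 4.4.6 sets out what is collected at each monthly visit. It begins with a general duty to record the previous month's resource use and then becomes specific: "the frequency and duration of inpatient hospitalization related to patient haemoglobinopathy will be recorded along with the primary reason for the hospitalization". Time spent in intensive care, general ward, emergency room or elsewhere is recorded for each stay. The section next defines the term without reference to cause: "Hospitalizations will be defined as any visit to the hospital requiring an overnight stay". Outpatient visits are counted with no cause limit. The last sentence is a catch-all: "Any resource used in addition to those foreseen in the protocol will be recorded".

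Section 7.3.28 refers back to Section 4.4.6 and lists the CRF parameters as "hospitalisation (ward, length of hospitalisation), outpatient visits (type of visit), tests performed outside those foreseen in the protocol". Section 11.10 states that resource use in each treatment group "will be summarized but will not be subjected to inferential statistics".

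**The concern.** The trial compares two chelators in patients with the same group of diseases. The stays most likely to separate the arms are those caused by the drugs, and a filter on relation to the disease puts exactly those stays in doubt. The documents attach different toxicities to the two drugs: Section 8 speaks of neutropenia induced by deferiprone, and Section 3.1 names renal impairment as a safety risk of deferasirox. Admission for neutropenia is expressly contemplated in Section 7.3.18: "provide protective isolation; if clinically indicated, admit patient to hospital".

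If sites treat such stays as unrelated to the haemoglobinopathy, bed-days by ward are missing from the resource data, and the shortfall need not be the same in both arms. Because the trial is open label (Section 6.5), the decision on relatedness is also made by staff who know the treatment, without any rule to guide them. At stake is whether the by-arm table for this secondary objective can be taken at face value.

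**Working it through.** No arithmetic applies: the plan gives no figure for resource use, and the point does not depend on alpha, power, margin or sample size. The check is a comparison of the texts.

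1. **Which stays are recorded.** The specific sentence in Section 4.4.6 limits inpatient stays to those linked to the haemoglobinopathy. Neither this section nor any other says whether a complication of chelation is linked in that sense. Two readings are open. On the narrow one, a drug reaction is not a manifestation of the blood disease, so the stay is left out. On the broad one, chelation treats iron overload from transfusions given for the disease, so the stay is counted.

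2. **Whether the definition settles it.** It makes any overnight stay a hospitalization. That fixes what a hospitalization is, while the sentence before it fixes which ones are recorded. The two have different scope, and nothing states which prevails.

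3. **Whether the catch-all settles it.** This depends on what being foreseen in the protocol means.
   - If it means anything the protocol mentions, admission for neutropenia is foreseen (Section 7.3.18) and falls outside the catch-all. Table 4 does not mention admission for renal, hepatic, skin or gastrointestinal toxicity, so those stays would fall inside it.
   - If it means scheduled by the protocol, every unplanned admission falls inside it, and the haemoglobinopathy qualifier has no effect.

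   The first meaning treats one toxicity differently from the others; the second cancels an explicit restriction. The catch-all also does not say that length of stay and ward are recorded for what it brings in.

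4. **Whether Section 7.3.28 settles it.** Its list has hospitalisation with ward and length and no cause limit. Its introduction refers to resources as reported in Section 4.4.6, so the limit may carry over. It omits the primary reason that Section 4.4.6 requires, and its only counterpart to the catch-all concerns tests.

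5. **Whether SAE reporting fills the gap.** Section 16.1 makes an event serious if it "requires hospitalisation or prolongation of existing hospitalization", whatever the cause, and Section 16.6 sends all confirmed neutropenia through the SAE route. The events are therefore captured for safety. No section says that SAE reports hold days by ward, or that they feed the summary in Section 11.10. The SAE form is not part of the documents, so recovery of bed-days from it cannot be assumed.

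6. **Consequence.** The text supports more than one recording rule. Between two limiting cases, all sites reading broadly and all sites reading narrowly, the omitted stays run from none to all toxicity admissions. If practice is mixed, the result depends on which sites enrol which patients and on the toxicity in each arm.

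**The case against.** The strongest reply is that this is loose wording and not an exclusion. Section 4.4.6 opens with a general duty to record, nowhere says that other stays are to be ignored, defines hospitalization without regard to cause, and ends with a catch-all. The CRF list, which sites would work from, has no filter. A reasonable investigator could count a chelation complication as related to the disease. The analysis is descriptive. Toxicity admissions appear in the SAE data, and Section 11.7 plans a summary of serious events and of events leading to dose change or discontinuation.

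Most of this stands, and it rules out three stronger readings that a reader might infer:

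- *That toxicity admissions necessarily drop out of the resource data.* This needs every site to read the qualifier narrowly and to set aside the definition, the catch-all and the CRF list. The documents are ambiguous on this and do not mandate it.
- *That the comparison is biased in favour of the more toxic drug.* That direction follows only if the narrow reading is applied uniformly. The documents name toxicity for both drugs and give no rates from which a net direction could be derived.
- *That a given number of bed-days is lost from one arm.* Any such number would rest wholly on assumed admission rates and lengths of stay, and placing the whole loss in one arm conflicts with the toxicities named for both.

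The reply does not remove the inconsistency itself. A descriptive table still misleads if its inputs are filtered by cause in some centres and not in others, and days by ward that were never entered cannot be relied on to be recoverable later.

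It is also fair to note that sorting stays by cause needs an unblinded judgement whoever does it. That applies to any breakdown by reason, including the one proposed here, but not to a count of all stays.

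**Conclusion.** The point holds as an internal inconsistency in the scope of data collection. Section 4.4.6 restricts inpatient stays by an undefined criterion that does not agree with its own definition, its catch-all or Section 7.3.28. Admissions for chelator toxicity may therefore be omitted or recorded unevenly, not necessarily to the same extent in both arms, and the by-arm summary in Section 11.10 may be distorted.

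The size is unknown and cannot be calculated from the documents. The reach is limited to a descriptive summary of a secondary objective. The primary analysis, the sample size and all formal tests are untouched, and the safety data still show these events. The conclusion assumes that at least some sites would apply the qualifier literally, and that the resource table is built from the resource CRF and not from SAE reports; the documents do not say otherwise. It is worth correcting because the remedy is small and the missing detail may not be recoverable afterwards.

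**What to change.** Delete the qualifier in Section 4.4.6 that ties inpatient stays to the patient's haemoglobinopathy. Record every overnight stay with ward, length and primary reason. Bring Section 7.3.28 into line by adding primary reason to its hospitalisation item, so that both sections state one rule.

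In the summary under Section 11.10, tabulate stays and days by arm in two ways: in total, which needs no judgement of relatedness, and by recorded primary reason (disease, study-drug adverse event, other). The disease-related subset that the current wording seems to want remains available from the second table.

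The cost is one phrase removed, slightly more data entry, and one extra split in a descriptive table. The split by reason will still be judged by unblinded staff, so the total should be read first.
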